This is a three-group randomized clinical trial that will compare: IM+PN v. IM alone v. brief detoxification with methadone (enhanced treatment as usual). IM will be provided in jail to opioid-dependent detainees who were not in MM treatment at the time of arrest, with transfer to 1 of 4 MMPs upon release. Participants will be assessed at baseline, 1, 3, 6, and 12 months post-baseline in terms of drug use, HIV risk, criminal behavior, arrest, and re-incarceration. A cost-benefit analysis will provide the information policymakers need for evidence-based decision-making. Moreover, an adequate sample of women will permit an examination of differential response by gender to the interventions. Qualitative interviews will explore the specific barriers to treatment entry in the community. The proposed study will yield novel results that can be used to inform public policy in instituting more effective and cost-effective approaches to the problem of post-release relapse to opioid use in jail detainees. Data collection will be harmonized with two other randomized trials of extended release naltrexone for detainees being conducted by NYU (in New York City) and UCLA (in Albuquerque, NM) among detainees with opioid dependence to permit analysis to answer questions that cut across the three cooperative studies.

Background and Significance

Opioid dependence among arrestees is a major problem throughout much of the developed world.^{40,41} Opioid-positive urine screening rates in major US city jails have ranged from 12% to 25%.⁴² In Baltimore, where there were almost 58,000 arrestees in 2011, more than 2,600 male and 1,100 female jail detainees required opioid detoxification.

Post-release Relapse is Frequent and Risky

Relapse rates to opioid use upon release from jail are extremely high. One study of heroin-addicted inmates in Rikers Island found that 70% relapsed within one week of release and 90% within one month.²² Recently-released inmates with opioid dependence face increased risk of overdose death,¹⁻³ and continued exposure to HIV³⁴ and hepatitis infection.⁴³ Relapse to heroin use undoubtedly plays a role in additional arrests, parole or probation violations, and return to incarceration.⁴⁴ Therefore, it is of considerable public health and public safety importance to develop approaches to engage arrestees in effective drug abuse treatment in the community and to assure continuity of care.

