It has long been recognized that women who are opioid-dependent face barriers to treatment entry⁶⁷ and have service needs that differ from those of men.⁶⁸⁻⁷⁰ Special individualized services such as PN, which has been used extensively with women for cancer screening, follow-up assessment, and treatment, have the potential to improve treatment entry and retention rates for women by addressing gender specific concerns,⁷¹ such as offering their significant others drug addiction treatment referral⁷²⁻⁷⁴ or making referrals for childcare or mental health treatment.⁷⁵ While the program initiating MM at Rikers Island has included women, the published data on outcomes for women in this treatment are sparse. In one study, women detainees were somewhat less likely than men to enter and remain in treatment following release.²² There are almost no data providing guidance on what services or procedures would increase the likelihood of successfully remaining in treatment following release from incarceration or the relative benefits that might be associated with such success. It is well known that the patterns and severity of criminal offenses committed by women differ significantly from those of men,⁷³ yet relatively little is known about whether there are changes in the frequency of criminal behavior or the severity of offenses associated with entry and retention in MM post-release. Because more than 1,100 women are treated for opioid withdrawal in the Baltimore City jail each year, the present study is designed to recruit a significant number of women to answer these treatment and cost-benefit questions.

APPROACH

1. Progress Report

The parent grant consisted of an original R01 and a competing continuation which produced 14 published papers in high impact journals (see **Publication List**); these papers had lasting impact on the treatment system in Baltimore and beyond. The most salient studies and findings are briefly summarized below:

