We decided not to include extended release naltrexone (XR-NTX), because its cost currently is prohibitive and because, unlike XR-NTX, methadone is widely available in community treatment programs throughout Baltimore and elsewhere in the US for continuing care post-release. We decided to include a detoxification arm as a comparison because virtually all jails in the US (including in Baltimore) use detoxification as their "treatment as usual." In doing so we will be affording a less distressing detoxification regimen (using methadone rather than clonidine) for the treatment-as-usual condition in Baltimore City (and elsewhere) because clonidine is considered inferior to methadone for symptom relief.⁹⁸ We decided that combining PN with detoxification was impractical because newly-released opioid-dependent detainees not on opioid agonists at the time of release, unlike those in the IM+PN and IM alone conditions who will be on medication and referred to one of 3 particular programs, would be very difficult for the PNers to track, engage, and link to the many different types of treatment programs available in Baltimore City. Finally, to maximize human subject protection and to exceed the services typically offered in jails, all study participants will be provided with enhanced treatment-as-usual (ETAU) including substance use, overdose and HIV prevention information, as well as Baltimore's Behavioral Health Systems central telephone intake and assessment line, to reduce their risk of relapse (see **Human Subjects**).

2. Study Sites

Baltimore City Pretrial and Detention Services. The Baltimore City Pretrial and Detention Services is a Division of Maryland's Department of Public Safety and Correctional Services (DPSCS). It operates three facilities on its downtown campus in Baltimore City including Central Booking, where all arrestees in Baltimore City are brought by police and the Men's and Women's Detention Centers (the sites of the proposed study). Annually, there are 57,925 arrestees (not unduplicated) that pass through Central Booking for processing and transfer to the Men's and Women's Detention Centers. The Men's Detention Center has 2,684 beds and the Women's Detention Center has 861 beds. The average length of stay in the Detention Centers is 42 days and individuals who are sentenced for more than a few months are transferred to prisons elsewhere.

3. Participants in the Proposed Research

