A total of 300 adult inmates (150 males and 150 females) will be enrolled in the study. We anticipate that participant characteristics will mirror the characteristics of the Baltimore City jail population from calendar year 2011, during which time there were 57,925 arrestees of whom 89% were African American, 10% were White, and 1% were other race; their mean age was 33. The majority of participants will be heroin-dependent; however, a small percentage are likely to be prescription opioid-dependent. In 2011, there were 2,622 men and 1,129 women (about 72 per week) who were not in opioid agonist treatment in the community at the time of arrest and who received opioid detoxification treatment in the Detention Centers with non-opioid medications. Given the large numbers of detainees receiving detoxification, it should be quite feasible to enroll 3-4 participants per week (less than 4% of the men and about 9% of the women who are treated for opioid withdrawal) and hence to complete participant recruitment in approximately 22 months.

3.a. Inclusion Criteria: (1) Meets DSM-5 criteria for opioid use disorder; (2) detained for at least 48 hours (because those detainees who are released quickly are most often released within 36 hours and hence would not have time to receive services in the study); (3) receiving opioid withdrawal treatment (as-usual) through the Detention Center's medical providers; (4) able and willing to provide informed consent in English; (5) detained for a charge that, if found guilty, will likely result in a sentence of less than 1 year; (6) plan to reside in Baltimore upon release; (7) 18 years of age and older.

3.b. Exclusion criteria: (1) enrolled in MM or buprenorphine treatment in the community at the time of arrest; (2) having a medical (liver failure, congestive heart failure) or psychiatric condition (e.g., suicidal ideation,

psychosis) that would make participation unsafe in the judgment of the medical staff or the PI; (3) pregnancy; (4) allergy to methadone; and, (5) requiring treatment for alcohol or sedative hypnotic withdrawal (i.e., in response to moderate or severe withdrawal).

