Modified World Mental Health Composite International Diagnostic Interview (CIDI) for Drug Use Disorders Revised. The updated version of the CIDI-2¹⁰⁷ (termed the World Mental Health CIDI [www.hcp.med.harvard.edu/wmhcdi/index.php]) will be used to determine whether individuals met the DSM-5 criteria for opioid and cocaine use disorders or remission during the one-month period prior to the 3, 6, and 12 month study assessments. The CIDI-2 was recommended by an expert panel of the NIDA CTN for gauging DSM-IV remission in clinical studies.¹⁰⁸ Its items can be used to determine DSM-5 criteria for substance use disorders. It will provide important and novel data that is complementary to self-reported drug use and urine testing data, and to the quality of life measurement, as an additional measure of change in functioning. It has been shown to have excellent reliability in diagnosing individuals with drug dependence.¹⁰⁹

Arrests and Incarcerations: In addition to self-reports, the official arrest and incarceration records will be obtained for 1 year prior and 1 year post-study enrollment from the Maryland Department of Public Safety and Correctional Services. These records can be used to gauge the severity of offenses, which may change even when arrest frequency remains about the same. We have successfully obtained and analyzed data of this nature in previous research.¹⁸

Risk Assessment Battery (RAB): The RAB is a brief questionnaire composed of 45 questions covering substance use and sexual HIV risk behaviors that has been extensively used with drug-dependent populations.¹³ The scale's drug-use risk and sex risk scores will be used as outcome measures.

World Health Organization Quality of Life (WHOQOL-BREF) is a brief 32-item instrument developed by the World Health Organization that has been used in a wide variety of populations internationally (Noerholm et al., 2004^{109c}; WHOQOL GROUP, 1998^{109d}; World Health Organization, 2004^{109e}) and has been found to have strong psychometric properties (O'Carroll et al., 2000^{109f}; Skevington et al., 2004^{109g}). The WHOQOL-BREF produces scores in four QOL domains: physical, psychological, social, and environmental. The WHOQOL-BREF also contains a single item, which is not incorporated into any of the four scale scores, asking participants to rate their overall QoL on a 5-point scale from very poor to very good.

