Substance Abuse Services Cost Analysis Program (SASCAP): Costs for each of the study conditions will be estimated using an activity-based costing approach which will allow cost estimation at the service level for study participants. To collect resource use and cost data necessary for activity-based costing, we will modify the SASCAP⁹⁰ to collect resource use and cost data for each condition necessary for activity-based costing. The SASCAP consists of a provider questionnaire administered once during the intervention phase to collect activity-level resource use and cost data for provider staff and nonlabor resources such as contracted services, building space, supplies and materials, and other miscellaneous resources (e.g., utilities). The SASCAP method reliably estimates the costs of specific treatment activities and the total cost per patient, and the investigators [name] and [name] have applied this micro-costing approach in other treatment studies.^{66,89,114,115} If a significant number of participants transition from the initial MMP to another MMP or buprenorphine treatment, costs for these treatments will also be determined.

AIM 1. To determine the relative effectiveness of IM+PN v. IM alone v. brief methadone detoxification (enhanced treatment-as-usual [ETAU]) for opioid-dependent detainees at 1, 3, 6, and 12 months post-release in terms of: (a) post-release treatment entry and retention; (b) illicit opioid and cocaine use; (c) meeting DSM-5 criteria of opioid and cocaine dependence; (d) HIV-risk behavior; and (e) criminal behavior, arrest, and days of incarceration.

Hypothesis 1A: The IM+PN and IM Alone conditions will have higher rates of treatment entry and longer retention, and concomitant lower rates of illicit opioid and cocaine use and of meeting DSM-5 criteria for opioid and cocaine use disorders, HIV risk behavior, criminal behavior, arrests, and days of incarcerations than will the Methadone Detoxification [ETAU] condition.

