Modified World Mental Health Composite International Diagnostic Interview (CIDI) for Drug Use Disorders. The updated version of the CIDI-2¹⁰⁷ (termed the World Mental Health CIDI [www.hcp.med.harvard.edu/wmhcdi/index.php]) will be used to determine whether individuals met the DSM-V criteria for opioid and cocaine dependence or remission during the one month period prior to the 3, 6, and 12-month assessments. The CIDI-2 was recommended by an expert panel of the NIDA CTN for gauging DSM-IV remission in clinical studies.¹⁰⁸ It has been shown to have excellent reliability in diagnosing individuals with drug dependence.¹⁰⁹ Its items can be used to determine DSM-5 criteria for substance use disorders.

Arrest and Incarcerations: In addition to self-reports, the official arrest and incarceration records will be obtained for 1 year prior and 1 year post-study enrollment from the Maryland Department of Public Safety and Correctional Services. These records can be used to gauge the severity of offenses, which may change even when arrest frequency remains about the same.

Risk Assessment Battery (RAB): The RAB is a brief questionnaire composed of 45 questions covering substance use and sexual HIV risk behaviors that has been extensively used with drug-dependent populations.¹³ The scale's drug-use risk and sex risk scores will be used as outcome measures.

Overdose AE Form. This brief 12 item questionnaire was devised for the present study to examine the number and characteristics and responses to any non-lethal overdoses between study visits.

Methadone Treatment Exposure Questionnaire. This brief 7 item questionnaire was devised for the present study to examine methadone treatment status, anticipated length of sojourn in methadone treatment, and reasons for leaving treatment (if applicable).

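### The official-records window starts at enrolment, during the index detention, and no rule excludes the index stay from days of incarceration or the index arrest from the prior-year count

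*Combined protocol and SAP*

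**What the plan says.** Under Measures for Aim 1 and 2, Arrests and Incarcerations, the plan states that "official arrest and incarceration records will be obtained for 1 year prior and 1 year post-study enrollment". Human Subjects, Research Information, repeats this. It is the only span given for the official records.

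Enrolment falls inside the index detention. Inclusion Criteria (3.a) require at least 48 hours of detention, Recruitment (4.b) takes place in the Detention Centers early in withdrawal treatment, and section 6.b has interim methadone (IM) participants stay on treatment in the jail up to release.

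The outcomes are mostly framed after release. Aim 1 compares the conditions "for opioid-dependent detainees at 1, 3, 6, and 12 months post-release in terms of" outcomes that include arrest and days of incarceration. The abstract lists "drug use, HIV risk, criminal behavior, arrest, and re-incarceration". Hypothesis 3c uses the 12 months after release. The abstract and the Project Timeline count follow-up from baseline instead, so the anchor is not consistent.

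No section gives a start date for days of incarceration or says how the index arrest and index stay are scored. The Economic Form 90, which collects nights incarcerated, has no such rule either. The Power paragraph tests arrest and incarceration by the planned contrasts alone, without a Time effect. Control Variables do not include prior arrests.

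**The concern.** Because enrolment falls inside the index detention, the enrolment date splits that episode in two. The index arrest lies in the year before. The rest of the index stay lies in the year after, which is the outcome year.

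Days of incarceration is an Aim 1 outcome under Hypotheses 1A and 1B. The remaining index stay depends mainly on charge and court, so counting it mixes days that treatment after release cannot change with those it might. A real reduction in re-incarceration then looks smaller in relative terms and is harder to detect. If the same records feed the incarceration part of Aim 3, index days enter the costing as well. Without a written rule, the analyst must either use the window as it stands or choose an exclusion once the data are visible.

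**Working it through.** No sample-size or power figure in the plan depends on this window, so there is no stated figure to reproduce. The check has three parts.

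**1. Window arithmetic.** Section 2, Study Sites, states: "The average length of stay in the Detention Centers is 42 days". That is the total stay of all detainees. Assume enrolment on day 2 to 7.
- Remaining index days = 42 − 7 to 42 − 2 = 35 to 40.
- Share of the outcome year = 35/365 to 40/365 = 9.6% to 11.0%.
- Post-release days covered by records = 365 − 40 to 365 − 35 = 325 to 330 of 365.

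So index days are counted, and the last 35 to 40 days of the 12 months after release have no records.

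**2. Noise and dilution.** The plan gives no re-incarceration rate or duration, so these are assumptions:
- remaining index stay exponential with mean *a* = 20 or 42 days, independent of arm. The value 42 takes the all-detainee mean as the remaining stay;
- probability of re-incarceration *p* = .4 to .6;
- days when re-incarcerated exponential with mean *m* = 60 to 150;
- everything capped at 365 days.

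Ignoring the cap, the variance ratio (all counted days to re-incarceration days alone) is VR = 1 + a² / [m² p(2 − p)]. For a = 42, p = .4, m = 60 this is 1 + 1764/(3600 × .64) = 1.77. Simulation handles the cap.

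Take a difference with power .90 on re-incarceration days at two-sided α = .01 (the plan's α). Its standardised size is 2.576 + 1.282 = 3.858. With index days included, power = Φ(3.858/√VR − 2.576). For VR = 1.77 this is Φ(2.900 − 2.576) = Φ(.324) = .63.

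A 30% reduction in re-incarceration days appears as 30% × (1 − index share).

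| a | p | m | Mean re-incarceration days | Index share | VR | Power | 30% appears as |
|---|---|---|---|---|---|---|---|
| 42 | .4 | 60 | 24 | 64% | 1.77 | .63 | 11% |
| 42 | .5 | 90 | 44 | 49% | 1.32 | .78 | 15% |
| 42 | .6 | 150 | 79 | 35% | 1.13 | .85 | 20% |
| 20 | .4 | 60 | 24 | 45% | 1.18 | .84 | 16% |
| 20 | .6 | 150 | 81 | 20% | 1.03 | .89 | 24% |

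This is a normal approximation. The planned count model would give somewhat different values.

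**3. Arrests.** The index arrest precedes enrolment, so it is not in the post-enrolment count. It adds one arrest per participant to the prior-year count. With one arrest per year before (excluding the index arrest) and one after, the true change is 0 and the recorded change is 1 − 2 = −1. The shift is the same in every arm, so it cancels between arms.

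**The case against.** The strongest reply is that the sentence says which records will be obtained, not how the outcome is scored. Re-incarceration by its meaning excludes the index stay, Aim 1 speaks of time after release, and if the records carry dates an analyst could remove the index episode. This stands in part: counting index days follows from using the window as written, and the plan never says that they count. But no other span is given for these records, and no scoring rule replaces it.

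Several stronger readings are tempting, and the documents do not support them.
- A reader might infer that the comparison between arms is biased, or that the measure is wrong for all 300 participants. Randomisation balances the remaining index stay in expectation, a participant released soon after enrolment adds almost no index days, and post-enrolment arrest counts do not contain the index arrest.
- A reader might infer that a planned change analysis is distorted. The Power paragraph specifies no Time effect for this outcome. The remark that offence severity is something "which may change even when arrest frequency remains about the same" describes a possible use of the records and sets no test. The background sentence on "whether there are changes in the frequency of criminal behavior or the severity of offenses associated with entry and retention" describes a gap in knowledge. Inclusion criterion 5 does limit the index charge, but no severity comparison is planned that this would bias.
- A reader might take the 42-day cases with 60 to 90 days of re-incarceration, where power is .63 to .78 for p of .4 to .5, as the expected loss. Those inputs are at the unfavourable end. Shorter remaining stays or longer re-incarcerations bring power to between .8 and .9.

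A further objection stands in full. Starting the count at release while records still end 365 days after enrolment would give participants unequal time at risk. Release also happens after randomisation, so a release-anchored outcome leaves unreleased participants without a value, against the plan's intent-to-treat approach. The fix has to deal with both.

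**Conclusion.** The point holds as a mismatch between the stated record window and the stated outcome. Used as written, the window puts the remaining index stay into days of incarceration. At the documents' 42-day mean stay and assumed enrolment on day 2 to 7, that is 35 to 40 days per participant. Under the assumed ranges, index days are about 20-64% of counted days and power of .90 falls to about .63-.89. The re-incarceration inputs are assumptions, and the 42 days refers to all detainees, so the size is uncertain. The direction, towards noise and dilution, does not depend on them.

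The effect is loss of precision and relative effect size, not bias between arms, unless assignment changes length of stay. The prior-year part is limited to descriptive before/after reporting. It should be corrected before the records are analysed, and does not threaten the trial's other outcomes.

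**What to change.** In Arrests and Incarcerations, and in the matching paragraph of Human Subjects, state that:
- days of incarceration count only custody that begins after first release from the index detention, and arrests are counted from that release. Specify release to the community, because sections 2 and 6.b allow transfer to other facilities;
- official records are pulled to 12 months after that release, so that every released participant has the same follow-up;
- the prior-year window is the 365 days ending the day before the index arrest, which excludes the index arrest and index stay;
- an enrolment-anchored analysis of all randomised participants is kept as a sensitivity analysis;
- length of the index stay and the number of participants not released are reported by arm.

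The cost is wording, a slightly wider record request at both ends, and one extra analysis. The timeline leaves room. Enrolment ends in month 28, so the last enrolment-anchored year ends in month 28 + 12 = 40, and records are obtained in months 41 to 48. Participants released too late to reach 12 months by the record pull should be listed by arm with those not released.
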